#### 4.1.2. Phase 2a General Inclusion Criteria

1. Patient must have an Eastern Cooperative Oncology Group (ECOG) Performance Score of 0 or 1.
2. Patient must be 18 years or older, of either sex, and of any race.
3. Patient (and/or parent/guardian for patients who otherwise are unable to provide independent consent) must be willing to give written informed consent and be able to adhere to dose and visit schedules.
4. Patient has had prior treatment for lymphoid malignancy requiring treatment for progressive disease/refractory disease (per guidelines for diagnosis and treatment of CLL [2] and revised response criteria for malignant lymphoma [3]).
5. Patient has had  $\geq 1$  prior systemic treatment regimen administered for at least 2 cycles (unless the patient was intolerant or experienced documented progression on therapy) that must have involved either: 1) an anti-CD20 agent (such as rituximab) WITH chemotherapy for B-cell NHL, unless contraindicated in the judgement of the investigator

(e.g., the patient was not a candidate for chemotherapy and received ibrutinib as first-line treatment); 2) a cytotoxic chemotherapy drug for T-cell NHL; 3) an anti-CD20 agent (such as rituximab) with chemotherapy for CLL, unless contraindicated in the judgement of the investigator (e.g., the patient was not a candidate for chemotherapy and received ibrutinib as first-line treatment); or 4) in patients with CD30-expressing PTCL, a CD30-directed antibody (e.g., brentuximab vedotin).

6. Female patients of childbearing potential and male patients must agree to abstain from sexual intercourse or to use an effective method of contraception during the study and for 90 days following the last dose of protocol therapy (examples of effective methods of contraception include oral contraceptives or double barrier methods such as condom plus spermicide or condom plus diaphragm). Patients enrolled into Cohort 2 should use effective contraception during treatment with rituximab and for 12 months after the last dose of rituximab.
7. Patient must have adequate bone marrow reserve as evidenced by an absolute neutrophil count (ANC)  $\geq 1,000/\mu\text{L}$ , platelet count  $\geq 75,000/\mu\text{L}$ . Platelet count must be without transfusion support within 7 days of the first dose of cerdulatinib.

*Note: CLL patients only: ANC  $\geq 750/\mu\text{L}$  and platelet count  $\geq 30,000/\mu\text{L}$  are acceptable. There are no limits on ANC or platelet count required for patients with leukemic forms of PTCL (ATLL, PLL, LGL) or HSTCL as long as cytopenia, if present, is secondary to disease.*

8. Patient must have adequate renal function as evidenced by a creatinine clearance  $\geq 30$  mL/min (calculated using the Cockcroft-Gault equation or based on a 24-hour urine specimen).
9. Patient must have adequate hepatic function as evidenced by a serum bilirubin level  $\leq 2.0$  mg/dL AND serum AST/ALT levels  $\leq 2.5\times$  the ULN for the reference lab. Serum bilirubin  $\leq 2.5$  mg/dL when increase clearly documented as due to Gilbert's syndrome.
10. Where available, ability to submit a formalin-fixed paraffin embedded tissue (FFPE) block or a minimum of 10 unstained, freshly cut FFPE tissue slides from lymph node or other biopsies that were collected as part of patient diagnosis. If samples are unavailable the patient is still eligible for enrollment.
11. Measureable disease for a given tumor type, defined as:
  - a. The presence of  $\geq 1$  lesion that measures  $\geq 1.5$  cm in a single dimension as assessed by CT, CT/PET for patients with nodal or mass lesions (e.g., FL, DLBCL, other NHL), or
  - b. Quantifiable circulating tumor cells for patients with circulating tumor (e.g., Sézary Syndrome [SS]), or
  - c. For CTCL: mSWAT score  $> 0$ .

12. Ability to provide redacted copies of pathology reports and radiology reports used for the diagnosis of NHL or CLL. In addition, for CTCL, ability to provide redacted photographs of skin responses.

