### 7.5.3. **Cerdulatinib and CYP3A4**

Cerdulatinib is a substrate for CYP3A4 and may also decrease expression levels of CYP3A4 enzyme activity in patients, thus potentially augmenting the AE profile of other drugs. To avoid possible drug-drug interactions, strong inhibitors, CYP3A sensitive substrates, and inducers of CYP3A4 should be avoided in patients receiving cerdulatinib. An inhibitor of CYP3A4 would reduce the metabolism of cerdulatinib and could result in high concentrations that could cause AEs. An inducer of CYP3A4 could result in lower than desired levels of cerdulatinib and lessen the likelihood of efficacy. Additionally, cerdulatinib can cause other medications to accumulate to levels that result in toxicity due to lower levels of CYP3A4 being expressed. Because of this effect CYP3A sensitive substrates need to be considered. If the Investigator feels that use of a strong inhibitor or strong inducer of CYP3A4 is necessary, this should be discussed with the Sponsor's Medical Monitor. [Appendix 3](#) provides a list of such CYP3A4 substrates and strong

inhibitors/inducers. Physicians should monitor for potential drug-drug interactions, and a dose adjustment (lowering) for CYP3A sensitive substrates should be considered on a case-by-case basis by the treating physician.

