### APPENDIX 3. STRONG CYP3A4 INHIBITORS AND INDUCERS AND CYP3A SENSITIVE SUBSTRATES

To avoid possible drug-drug interactions, strong inhibitors and inducers of CYP3A4 and CYP3A sensitive substrates should be avoided in patients receiving cerdulatinib (Table A3-9 and Table A3-10). If the Investigator feels that use of these medications is necessary, this should be discussed with the Medical Monitor. A dose adjustment (lowering) for CYP3A sensitive substrates may be considered on a case-by-case basis.

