**Table A3-10: CYP3A Sensitive Substrates**

Generic (Trade Name)	
Albendazole (Albenza®)	Levomilnacipran (Fetzima®)
Alfentanil (Alfenta®) - drug has narrow therapeutic index	Lopinavir and Ritonavir (Kaletra®)
Aliskiren (Tekturna®)	Lovastatin (Mevacor®)
Almotriptan (Axert®)	Lurasidone (Latuda®)
Alprazolam (Xanax®)	Maraviroc (Selzentry®)
Aprepitant (Emend®)	Medroxyprogesterone acetate (Depo-Provera®)
Aripiprazole (Abilify®)	Methadone
Avanafil (Stendra®)	Midazolam (Versed®)
Brexpiprazole (Rexulti®)	Mirtazapine (Remeron®)
Bromocriptine (Cycloset®, Parlodel®)	Nevirapine (Viramune®)
Budesonide (Entocort®, Pulmicort®)	Nisoldipine (Sular®)
Buprenorphine (Suboxone®, Butrans®, etc.)	Ospemifene (Osphena®)

Generic (Trade Name)	
Buspirone (Buspar®)	Oxycodone (Percocet®, Oxycontin®)
Cariprazine (Vraylar®)	Paritaprevir (Viekira Pak™, Technivie™) - major substrate
Clonazepam (Klonopin®) (probable)	Pimozide (Orap®) - drug has narrow therapeutic index
Conivaptan (Vaprisol®)	Praziquantel (Biltricide®)
Cyclophosphamide (Cytosan®)	Propafenone (Rythmol®)
Cyclosporine (Neoral®, Gengraf®, Sandimmune®) - drug has narrow therapeutic index	Quetiapine (Seroquel®)
Daclatasvir (Daklinza™)	Quinidine - drug has narrow therapeutic index
Darifenacin (Enablex®)	Roflumilast (Daliresp®)
Darunavir (Prezista®)	Salmeterol (Serevent®)
Dasatinib (Sprycel®)	Saquinavir (Invirase®)
Diazepam (Valium®)	Sildenafil (Viagra®)
Dienogest (progesterone in oral contraceptives)	Simeprevir (Olysio®)
Dihydroergotamine (DHE-45®, Migranal®) – drug has narrow therapeutic index	Simvastatin (Zocor®)
Dronedarone (Multaq®)	Sirolimus (Rapamune®) - drug has narrow therapeutic index
Drospirenone (progesterone in oral contraceptives)	Suvorexant (Belsomra®)
Elbasvir (Zepatier®)	Tacrolimus (Prograf®) - drug has narrow therapeutic index
Eletriptan (Relpax®)	Tadalafil (Cialis®)
Eplerenone (Inspra®)	Tamsulosin (Flomax®)
Ergotamine (Cafegot®)	Temsirolimus (Torisel®)
Eszopiclone (Lunesta®)	Ticagrelor (Brilinta®)
Ethinyl Estradiol (oral contraceptives, Ortho Evra®, NuvaRing®)	Tinidazole (Tindamax®)
Etonogestrel (Implanon®, Nexplanon®, NuvaRing®)	Tofacitinib (Xeljanz®) (major substrate)
Everolimus (Afinitor®)	Tolvaptan (Samsca®)
Felodipine (Plendil®)	Tipranavir (Aptivus®)
Fentanyl (Duragesic®) - drug has narrow therapeutic index	Triazolam (Halcion®)
Flibanserin (Addyi®) - major substrate	Vardenafil (Levitra®)
Fluticasone (Flovent®, Arnuity Ellipta®)	Verapamil (Calan®, Covera-HS®, Verelan®, etc.)

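### Inclusion 6 offers oral contraceptives as an example method with no cross-reference, while Section 7.5.3 and Appendix 3 advise against CYP3A sensitive substrates on cerdulatinib and Table A3-10 lists oral-contraceptive hormones

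*Protocol*

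**What the plan says.** **Inclusion 6 (Protocol 4.1.2; same wording in the synopsis).** Women of childbearing potential, and men, must abstain or use an effective method during the study and for 90 days after the last dose. The "examples of effective methods of contraception include oral contraceptives", followed by double barrier methods as the alternative. No cross-reference to Section 7.5.3 or Appendix 3 is given.

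**Section 7.5.3.** To limit drug interactions, "strong inhibitors, CYP3A sensitive substrates, and inducers of CYP3A4 should be avoided in patients receiving cerdulatinib". The reason given is that cerdulatinib may lower CYP3A4 and so let other drugs accumulate. For substrates the section adds that "a dose adjustment (lowering) for CYP3A sensitive substrates should be considered on a case-by-case" basis, by the treating physician. Its sentence on consulting the Medical Monitor names only strong inhibitors and strong inducers.

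**Appendix 3.** The same advice is repeated: "strong inhibitors and inducers of CYP3A4 and CYP3A sensitive substrates should be avoided in patients receiving cerdulatinib". The exception here is wider and takes in the substrates: "If the Investigator feels that use of these medications is necessary, this should be discussed with the Medical Monitor".

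**Table A3-10.** The substrate list includes "Ethinyl Estradiol (oral contraceptives" and other combined products), "Drospirenone (progesterone in oral contraceptives") and "Dienogest (progesterone in oral contraceptives"). It also lists etonogestrel and medroxyprogesterone acetate.

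**Exclusion 4 (Section 4.2).** A patient who needs a CYP3A4-sensitive substrate long term is excluded, and Appendix 3 is cited.

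**The concern.** A woman of childbearing potential who takes a combined pill satisfies inclusion 6 through one of the methods it names. The components of that pill are on the list that Section 7.5.3 and Appendix 3 advise against. Inclusion 6 gives the site no prompt to look at that list or to start the Medical Monitor discussion that Appendix 3 asks for. Exclusion 4 leaves room for a further difference: one site could read long-term pill use as chronic treatment with a listed substrate, and another could read it as the contraception the protocol requested. The two sites would then treat the same woman differently.

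The safety question, on the protocol's own reasoning, is higher hormone exposure if CYP3A4 activity falls. Contraception lasts as long as treatment, and treatment can continue until progression or intolerable toxicity (Section 3.1.4), so exposure would not be brief. Response rate, sample size and error rates are not at stake.

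**Working it through.** The main check is a comparison of texts. No design figure has to be reproduced.

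1. **Is the example qualified anywhere?** Inclusion 6 reads the same in Section 4.1.2 and in the synopsis, without qualifier or cross-reference. Section 7.5.1 (prohibited medications) mentions neither contraceptives nor CYP3A substrates. No other section says how hormonal contraceptives are handled in female patients.

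2. **Is the link between the pill and the list explicit?** Yes. Five entries in Table A3-10 are contraceptive hormones: ethinyl estradiol, drospirenone, dienogest, etonogestrel and medroxyprogesterone acetate. The table itself labels three of them (the first three) as oral-contraceptive components.

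3. **What route is open if a listed agent is used?** Three texts give three answers:
   - Appendix 3: discuss with the Medical Monitor if use is felt necessary; lowering the substrate dose may be considered case by case.
   - Section 7.5.3: the treating physician considers lowering the substrate dose; the Medical Monitor is mentioned only for strong inhibitors and inducers.
   - Exclusion 4: a need for chronic treatment excludes the patient.

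4. **How plausible is an interaction at the Phase 2a doses?** Inputs: Section 1.2 reports lower CYP3A4 mRNA and activity at 0.3 to 1 µM cerdulatinib, and 89.5% binding in human plasma. Table 7 gives the concentrations at the three starting doses (observed at 20 mg, modelled at 25 and 30 mg).
   - Unbound fraction = 1 − 0.895 = 0.105. Unbound concentration = total × 0.105.
   - Values in µM, ordered Cmin, Cave, Cmax:
     - 20 mg BID: total 0.38, 0.52, 0.89; unbound 0.040, 0.055, 0.093
     - 25 mg BID: total 0.66, 0.75, 0.89; unbound 0.069, 0.079, 0.093
     - 30 mg BID: total 0.83, 1.0, 1.09; unbound 0.087, 0.105, 0.114
   - If 0.3 to 1 µM refers to total concentration, 8 of 9 values lie in the range and one (1.09) lies just above it.
   - If it refers to unbound concentration, 0 of 9 values reach it.

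   The protocol does not say which applies, so both are shown. It gives no fold-change for any substrate. The evidence therefore runs from no interaction shown to a plausible one.

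5. **What would catch use in practice?** The sponsor or its designee reviews eligibility documents before assigning a patient number (Section 4.3). Appendix 1 schedules eligibility review at Screening and Cycle 1 Day 1, and concomitant-medication review at Screening and on Days 1, 8 and 15 of Cycle 1. Section 7.1.4 has medications recorded throughout, and Section 7.3.2 has them assessed on Day 1 of every cycle. These checks may reveal use, but they do not say which instruction governs once it is found.

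**The case against.** The best defence is that no real conflict exists. Inclusion 6 deals with willingness to prevent pregnancy; drug interactions are dealt with elsewhere. It offers abstinence first, then examples joined by *or*, and requires no hormone. It also covers men, for whose partners the pill is a natural example. The avoidance is advisory, and Table A3-10 is broad enough to include oxycodone, zolpidem and fluticasone, so it works as a caution list. Section 7.5.3 already tells physicians to monitor for interactions. Exclusion 4 sits beside the inclusion criteria and cites Appendix 3, and the checks in step 5 add further chances to notice.

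Much of this stands. A reader might infer that the protocol steers women to a prohibited drug, or makes the pill the default method. The documents do not support that: the pill is one of several examples, and the list is not a ban. What survives is narrower. For a female patient, one section presents a method as acceptable, another names its components as drugs to avoid, and nothing connects the two.

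A second objection is that moving women from oral to barrier methods may reduce contraceptive reliability. That is a fair caution, and it is a reason to keep the pill among the examples and available after discussion.

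**Conclusion.** The inconsistency is real, in current text, and small. It is a cheap improvement and not a defect in the efficacy design. The textual finding needs no assumption about the size of the interaction, because the protocol has already chosen to advise avoidance. The number of women of childbearing potential is not given; that it is small is an assumption.

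Three stronger readings should be set aside:

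- **That the interaction is established.** Section 1.2 calls it possible, and the count of 8 of 9 concentrations in range falls to 0 of 9 if the range is unbound.
- **That contraception would fail.** The mechanism described is lower CYP3A4 and accumulation of the substrate, which points to more hormone exposure.
- **That exclusion 4 bars every woman who follows inclusion 6 with a pill.** This depends on how requiring chronic treatment is read, and other methods are open to her. The wording permits the question but does not settle it.

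Female partners of male patients do not take cerdulatinib and are not affected.

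**What to change.** Make three short edits, with the first two carried into the synopsis:

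1. **Inclusion 6.** Keep the present examples and add: *For female patients receiving cerdulatinib, hormonal contraceptives containing an agent listed in Table A3-10 should be avoided where another effective method is suitable; if use is considered necessary, it should be discussed with the Medical Monitor (Appendix 3). This does not apply to female partners of male patients.*
2. **Exclusion 4.** Add a clause saying that a hormonal contraceptive used after that discussion is not by itself exclusionary.
3. **Section 7.5.3.** Extend the Medical Monitor sentence to sensitive substrates, so that it matches Appendix 3.

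The wording stays at discussion, which is the standard Appendix 3 already sets, and adds no approval step. Data collection and analysis do not change. The downside is a slightly narrower contraceptive choice for a few women. Barrier methods may also be less reliable, which is why the listed hormones remain available after Medical Monitor discussion.

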#### **4.1.3. Phase 2a Cohort-specific Inclusion Criteria**

##### **4.1.3.1. Cohort 1 (FL) – Grades 1 to 3A (Single-agent Cerdulatinib)**

1. Received  $\geq 1$  prior treatment regimen.

##### **4.1.3.2. Cohort 2 (Combination) – FL, Grades 1 to 3A (Cerdulatinib + Rituximab)**

1. Received  $\geq 1$  prior treatment regimen.

##### **4.1.3.3. Cohort 3 (aNHL) – aNHL (Single-agent Cerdulatinib)**

Aggressive non-Hodgkin lymphoma (aNHL) is defined as DLBCL, FL Grade 3B, Mantle Cell Lymphoma (MCL), and transformed NHL.

1. Relapsed from  $\geq 1$  but  $\leq 3$  prior cytotoxic chemotherapy regimens with an anti CD20 antibody, (e.g., R-CHOP, BR). Patients must have received an anthracycline based therapy unless anthracyclines were deemed inappropriate in the judgement of the investigator. Patients must have either relapsed following autologous stem cell therapy (ASCT), or not be candidates (ineligible) for ASCT, defined as meeting any of the following criteria [1]:
  - a. Age  $\geq 70$  years.
  - b. Carbon monoxide diffusion capacity (DLCO)  $< 50\%$  by pulmonary function tests.
  - c. Forced expiratory volume in 1 second/forced vital capacity FEV1/FVC  $< 60\%$  predicted by pulmonary function tests.
  - d. Left ventricular ejection fraction (LVEF)  $< 45\%$  by multiple gated acquisition (MUGA) or echocardiogram.
  - e. Uncontrolled arrhythmia.
  - f. Calculated creatinine clearance (Cockcroft-Gault)  $\leq 60$  mL/min.
  - g. Other comorbidities (e.g., medical conditions or psychosocial conditions) that would likely result in an unacceptably high probability of treatment/transplant related morbidity and mortality in the judgement of the investigator (e.g., high Hematopoietic Cell Transplantation Co-Morbidity Index [HCT-CI], Cumulative Illness Rating Scale [CIRS] scores).
  - h. Refusal of ASCT.

Note: Antibody drug conjugates (ADC) count as cytotoxic chemotherapy. Salvage chemotherapy prior to ASCT with or without maintenance therapy counts as one regimen.

**4.1.3.4. Cohort 4 (CLL/SLL) – CLL/SLL (Single-agent Cerdulatinib)**

1. Received  $\geq 1$  prior treatment regimen.

**4.1.3.5. Cohort 5 (PTCL NHL) – Peripheral T-cell NHL (PTCL) (Single-agent Cerdulatinib)**

1. Received  $\geq 1$  prior systemic treatment regimen for PTCL. In patients with CD30-expressing PTCL, prior treatment must include a CD30-directed antibody (e.g., brentuximab vedotin).

**4.1.3.6. Cohort 6 (CTCL NHL)– Cutaneous T-cell NHL (CTCL, MF/SS only) (Single-agent Cerdulatinib)**

1. Received  $\geq 1$  prior systemic treatment regimen for CTCL.

**4.2. Phase 1 and Phase 2a Exclusion Criteria**

A patient meeting any 1 of the Exclusion Criteria listed below will be excluded from the trial.

1. Patient has Richter's syndrome, Burkitt's lymphoma, or Burkitt-like Lymphoma. Patients with transformed DLBCL from Follicular NHL are eligible.
2. Patient has undergone prior allogeneic or autologous transplant with infusion of stem cells within 90 days before Cycle 1 Day 1 (C1D1), or on active immunosuppressive therapy for graft-versus-host disease (GVHD) or GVHD prophylaxis within 8 weeks before C1D1.
3. Patient has received prior therapy with a spleen tyrosine kinase (SYK) inhibitor.
4. Patient requires chronic treatment with a strong CYP3A4 inhibitor or inducer or CYP3A4-sensitive substrate ([Appendix 3](#)).
5. Patient has known lymphomatous involvement of the central nervous system (CNS).
6. Patient has a known hypersensitivity to any of the components of cerdulatinib.
7. Patient has persistent, unresolved NCI-CTCAE v5.0  $\geq$  Grade 2 clinically significant (in the judgement of the investigator) drug-related toxicity (except alopecia, erectile impotence, hot flashes, libido, neuropathy) associated with previous treatment.
8. Prior monoclonal antibody (mAb) (including alemtuzumab), radioimmunoconjugate, antibody drug conjugate (ADC), phototherapy, radiotherapy, chemotherapy, immunotherapy, immunosuppressive therapy, or any investigational agent for the purposes of treating cancer within 3 weeks before Cycle 1 Day 1.
9. For CTCL patients only: total skin electron beam therapy (TSEBT) within 12 weeks, or initiation of topical steroid, nitrogen mustard, or topical retinoid within 2 weeks before Cycle 1 Day 1. Patients with CTCL who are on a stable topical regimen for  $\geq 4$  weeks prior to C1D1 are allowed.

10. The patient has a known infection with HIV, HBV, or HCV or is a carrier of HBV or HCV. Patients who are seropositive for HCV antibody must test negative for HCV by PCR assay to be eligible. Patients with an occult or prior HBV infection (defined as being seropositive total hepatitis B core antibody [HBcAb] and seronegative for HBsAg) may be included if his or her HBV DNA is undetectable or if it is undetectable with antiviral therapy. These patients must be willing to undergo additional testing per local standard of care if this data is unavailable. Additional testing will be performed if the patient does not have documentation of a negative hepatitis panel and a negative HIV history within the 12-week period prior to enrollment.
11. Patient has an active infection requiring systemic treatment, defined as requiring antimicrobial, antifungal, or antiviral agents. Prophylactic antimicrobial treatment is permitted.
12. Patient has significant gastrointestinal disease that may interfere with absorption of the study drug or that predisposes him/her to GI adverse effects, or has had major gastric or bowel surgery.
13. Patient has difficulty swallowing or malabsorption syndrome.
14. Patient has any other medical, social, or psychiatric condition that might interfere with the patient's participation in the trial or interfere with the interpretation of trial results.
15. Patient has undergone major surgery within 4 weeks prior to first study drug administration.
16. Patient has a history (within 2 years prior to first study drug administration) of another malignancy unless malignancy treated with curative intent and likelihood of relapse is small (< 5% in 2 years in the judgement of the investigator). Patients with a history of squamous or basal cell carcinoma of the skin or carcinoma in situ of the cervix may be enrolled.
17. Patient is receiving systemic steroids at doses greater than the equivalent of prednisone, 20 mg daily, with the exception of intermittent use for the treatment of emesis.
18. Patient is female and is breast-feeding, pregnant, or intends to become pregnant.
19. Patient is participating in any other therapeutic clinical study (observational or registry trials are allowed).

